## **7.4 Routine Adverse Event Reporting**

All Adverse Events **must** be reported in routine study data submissions to the Overall PI on the toxicity case report forms. **AEs reported through expedited processes (e.g., reported to the IRB, FDA, etc.) must also be reported in routine study data submissions.**

## **8. PHARMACEUTICAL INFORMATION**

A list of the adverse events and potential risks associated with the investigational or other agents administered in this study can be found in Section 7.1.

N/A

## **9. BIOMARKER, CORRELATIVE, AND SPECIAL STUDIES**

N/A

### **9.1 Biomarker Studies**

N/A

### **9.2 Laboratory Correlative Studies**

N/A

### **9.3 Special Studies**

N/A

## 10. STUDY CALENDAR

Section	Baseline	6 week (+/- 2 weeks) visit*	12 week visit	EDC Timepoints
PSCR counseling	X	X	X	Baseline, 6 week, 12 week
Informed consent	X	X	X	Baseline, 6 week, 12 week
Demographics	X			Baseline, 6 week, 12 week
Medical history	X	X	X	Baseline, 6 week, 12 week
MEK, BRAF, or Pan-RAF inhibitor dosing	X	X	X	Baseline, 6 week, 12 week
Skin exam and interview	X	X	X	Baseline, 6 week, 12 week
Severity Scores Completed	X	X	X	Baseline, 6 week, 12 week
Adverse events evaluation	X	X	X	Baseline, 6 week, 12 week

\*6 week visit may be conducted virtually on request. Photographs will be requested prior to visit.

## 11. MEASUREMENT OF EFFECT

The measurement is the proportion (percentage) of patients with one or more cutaneous reaction to targeted BRAF, MEK or Pan-RAF inhibitor therapy. Secondary outcome measures include number of different cutaneous reactions experienced by each patient, severity of cutaneous reactions measured by the Common Terminology Criteria for Adverse Events (CTCAE), severity of xerosis measured by the Overall Dry Skin Score (ODS), severity of hand foot syndrome measured by the Hand-Foot Skin Reaction and Quality of Life Score (HFS-14), Pediatric Quality of Life Inventory General Well-Being Scale (PedsQL), and the Children's Dermatology Life Quality Index (CDLQI). To view these assessments and scoring in detail, please see Appendix A.

### 11.1 Antitumor Effect – Solid Tumors

N/A

#### 11.1.1 Disease Parameters

Any new or changing skin, hair or nail findings

#### 11.1.2 Methods for Evaluation of Disease

All measurements should be taken and recorded in metric notation using a ruler, calipers, or a digital measurement tool. All baseline evaluations should be performed as closely as possible to the beginning of treatment and never more than 4 weeks before the beginning of the treatment.

The same method of assessment and the same technique should be used to characterize each identified and reported lesion at baseline and during follow-up. Imaging-based evaluation is preferred to evaluation by clinical examination unless the lesion(s) being followed cannot be imaged but are assessable by clinical exam.

Clinical lesions. In the case of skin, hair or nail lesions, documentation by color photography, including a ruler to estimate the size of the lesion, is recommended.

#### 11.1.3 Response Criteria

Severity of skin reactions will be graded according to the following severity scoring systems:

Common Terminology Criteria for Adverse Events (CTCAE) (Appendix A)  
Overall Dry Skin Score (ODS) (Appendix B)  
Hand-Foot Skin Reaction Quality of Life Score (HFS-14) (Appendix C)  
Children's Dermatology Life Quality Index (CDLQI) (Appendix D)  
Pediatric Quality of Life Inventory (PedsQL)

#### 11.1.4 Response Review

Skin exams will be performed by dermatologists and trained research staff.

### 12. DATA REPORTING / REGULATORY REQUIREMENTS

Adverse event lists, guidelines, and instructions for AE reporting can be found in Section 7.0 (Adverse Events: List and Reporting Requirements).

#### 12.1 Data Reporting

Data will be reported in REDCap. The original plan was for each of the three sites to independently activate the protocol, and have their own separate, but identical, REDCap electronic case report forms (eCRFs). Each site has its own separate IRB approval for the trial. However, during study conduct, paper CRFs from the other two sites were sent to BCH, and the other sites' data were entered into the BCH REDCap eCRFs. All data for the trial currently reside at BCH; the existence of data at BCH is covered by two legal Data Sharing Agreements. All data is labeled by site. Keeping data transcribed as is will facilitate statistical analysis, and minimize further efforts towards data transfer.

### 13. STATISTICAL CONSIDERATIONS

Descriptive analysis of this cohort, including data from three sites, will be performed.

#### 13.1 Study Design/Endpoints

The primary outcome measure is cutaneous reaction to targeted BRAF, MEK, or Pan-RAF inhibitor therapy. Secondary outcome measures include number of different cutaneous reactions experienced by each patient, severity of cutaneous reactions measured by the Common Terminology Criteria for Adverse Events (CTCAE), severity of xerosis measured by the Overall Dry Skin Score (ODS), severity of hand foot syndrome measured by the Hand-Foot Skin Reaction and Quality of Life Score (HFS-14), Pediatric Quality of Life Inventory (PedsQL), and the Children's Dermatology Life Quality Index (CDLQI).

#### 13.2 Sample Size, Accrual Rate and Study Duration

Sample Size: 22 participants from three sites (DFCI [8], Toronto Sick Kids [7], Lurie Children's Hospital [7])

Accrual Rate: 6 participants / 1 year

Study duration: ~3 years (3 years of accrual + 12 weeks of treatment on the last patient enrolled)

This sample size is limited due to the rare nature of these cancers, but a total of 22 will be sufficient for descriptive analyses. The study team believes that accrual of more than 8 patients in a one year period at DFCI/BCH\*\*\* is not feasible.

#### 13.3 Stratification Factors

N/A

### **13.4 Interim Monitoring Plan**

N/A

### **13.5 Analysis of Primary Endpoints**

In the overall cohort, the proportion of patients with one or more cutaneous reactions will be calculated, and a 95% exact confidence interval will be placed on this proportion.

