### 1.1 Study Design

This prospective, single-arm phase 2 clinical trial will be performed at Dana-Farber Cancer Institute/Boston Children's Hospital\*\*\*. Additional external sites will conduct the same study concurrently. Data from all sites will be pooled at the end of the study and a meta-analysis of all aggregated data will be performed. IRB approval will be obtained prior to initiation of the study. This study will include patients receiving MEK inhibitor, BRAF inhibitor or pan-RAF inhibitor therapies for CNS and PNS tumors. At this time, we do not have the personnel or funding required to coordinate with multiple departments to identify all patients receiving these therapies.

Baseline data will be obtained from each participant via medical record review, if applicable. Baseline data includes, but is not limited to the following: general demographic data (age at tumor diagnosis, gender, race), type of primary tumor, type of therapy regimen (targeted therapy agents/dose/duration, chemotherapy agents/dose/duration, radiation field location/size/dose), past and current immunosuppressive medications, secondary malignancies including melanoma and nonmelanoma skin cancer, and family history of skin diseases.

All patients will undergo skin examinations at the initial study visit, mid-study visit (6 weeks (+/- 2 weeks)), and at 12 weeks after treatment initiation. Weight-based dosing of MEK, BRAF, or Pan-RAF inhibitor therapies will be recorded at each visit. If any skin findings are present, patients and families will be asked about the timing, frequency, location and severity of these skin findings.

Patients will undergo a full mucocutaneous physical examination including skin, mucous membranes, hair, and nails during their dermatology visit. Abnormalities will be carefully documented, including degree of involvement (% body surface area, number of nails, % of scalp).

Patients receiving targeted therapy will be evaluated specifically for the following skin reactions, previously reported in the literature: follicular skin rash, acneiform skin eruption, cheilitis, xerosis, hand foot syndrome, eruptive nevi (defined as > 5 new nevi over a 3 month period), keratoacanthoma, squamous cell carcinoma, photosensitivity. Undefined skin reactions will also be recorded.

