Patients will be asked to keep a diary of their daily skin care regimen and every-other-day dilute bleach baths including what products they used, how the bleach bath was made and how long they soaked in the bleach bath. This diary will be used to measure compliance.

If any patients develop a skin reaction to dilute bleach, they will discontinue and it will be documented.

If any patients develop a skin reaction to a moisturizer or sunscreen, we will recommend an alternative product, as we would do clinically.

Products mentioned above to be utilized in the preventative skin care regimen will be paid for by the Dermatology Research Fund at the Jimmy Fund Clinic\*\*\*. External sites will supply their own sample products to participants.

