### **7.1.1 Adverse Event List(s) for Commercial Agent(s)**

Commercial agents for preventative skin care routines include gentle soaps, lotions, cleansers, moisturizers, and sunscreen. Adverse events from these agents may include skin irritation. Patients will be referred to product information included with purchase of these products for possible adverse events.

Commercial agents for dilute bleach bath include OTC bleach, with 1/4 cup to be placed into a 1/2 full bathtub. Adverse events from this commercial agent may include eye irritation if contact with eyes and possible skin irritation. Patients will be

instructed to carefully avoid eye contact with bath water during dilute bleach baths and will be instructed to stop dilute bleach bath if skin irritation occurs following bleach baths.

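### Does Section 13 need a written rule to separate skin reactions to the bleach baths and skin-care products from reactions to the targeted drug?

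*Combined protocol and SAP*

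**What the plan says.** The outcome is defined by cause. Section 13.1 states: "The primary outcome measure is cutaneous reaction to targeted BRAF, MEK, or Pan-RAF inhibitor therapy". Section 11 agrees: "The measurement is the proportion (percentage) of patients with one or more cutaneous reaction to targeted BRAF, MEK or Pan-RAF inhibitor therapy". All three objectives in Section 1 use the same limit.

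The analysis sentence in Section 13.5 is shorter: "the proportion of patients with one or more cutaneous reactions will be calculated", with a 95% exact interval. It names no cause, and neither does Section 13.6 for the number of reactions per patient or the CTCAE grades. Section 11.1.1 casts a wide net, "Any new or changing skin, hair or nail findings", and Section 1.1 adds, after its list of known reactions, "Undefined skin reactions will also be recorded".

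The regimen can also affect the skin. Section 7.1.1 says of bleach: "Adverse events from this commercial agent may include eye irritation if contact with eyes and possible skin irritation". It lists skin irritation for the skin-care products too. Section 5 says: "If any patients develop a skin reaction to dilute bleach, they will discontinue and it will be documented". It also provides for a change of product "If any patients develop a skin reaction to a moisturizer or sunscreen". Section 7.2 grades how each adverse event relates to the study treatment. Sections 13.7, 13.7.1 and 13.7.2 are marked not applicable.

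**The concern.** Every child receives the drug and the regimen together, and both can produce irritated, dry or red skin. The outcome depends on cause, but the sentence that turns data into a proportion does not mention cause, and nothing ties the Section 7.2 attribution to Section 13. One analyst might count every skin finding. Another might drop those put down to bleach.

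At stake is the trial's main result. Counting a bleach reaction as a drug reaction raises the primary proportion. Putting a drug reaction down to bleach lowers it. Only children without a drug reaction can be added wrongly, so the ambiguity is small when nearly all children react to the drug. It grows if the regimen prevents reactions, which is what the trial hopes to see.

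**Working it through.** **1. Inputs.** N = 22, from 8 + 7 + 7 at three sites (Section 13.2), which agrees with the stated total. The background proportion with a reaction is 21/22 = 95.5% (Section 2). The interval is exact at 95% (Section 13.5), taken as Clopper-Pearson. The documents give no rate of skin reaction to the regimen, and no power, target width or decision threshold, so there is no planned figure to reproduce for this endpoint.

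**2. Which text governs the count.** Section 13.5 is the analysis of the primary endpoint, and 13.1 of the same chapter says what that endpoint is. An any-cause count requires setting 13.1 aside, together with Section 11 and the objectives. Sections 11.1.1 and 1.1 tell examiners what to look for and record. Neither says that everything recorded enters the numerator.

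**3. Effect per child.** A child whose only finding is a regimen reaction moves the proportion by 1/22 = 4.5 points. The most children who can be added wrongly is 22 minus the number with a drug reaction: 1 at 21/22, and 5 at 17/22.

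| Children counted | Proportion | 95% exact CI |
|---|---|---|
| 17/22 | 77.3% | 54.6 to 92.2 |
| 18/22 | 81.8% | 59.7 to 94.8 |
| 19/22 | 86.4% | 65.1 to 97.1 |
| 20/22 | 90.9% | 70.8 to 98.9 |
| 21/22 | 95.5% | 77.2 to 99.9 |
| 22/22 | 100% | 84.6 to 100 |

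At the background proportion, the choice is between the last two rows. If 17 children react to the drug (assumed) and one, two or three others have only regimen irritation (assumed), the first row becomes the second, third or fourth. Even the largest of these, 90.9%, lies inside the interval around 77.3%.

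**4. How likely is it to arise?** Let p be the share with a drug reaction and q the share with a regimen reaction. Assume the two are independent, with q between 5% and 30%. The expected addition is (1 − p)q. The chance that at least one child's status depends on the rule is 1 − [1 − (1 − p)q]^22.

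| p | Expected addition, q = 5% to 30% | Chance at least one child is affected |
|---|---|---|
| 95.5% | 0.2 to 1.4 points | 5% to 26% |
| 80% | 1 to 6 points | 20% to 74% |
| 50% | 2.5 to 15 points | 43% to 97% |

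For example, at p = 80% and q = 5%, (1 − p)q = 0.01 and 1 − 0.99^22 = 0.198.

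**5. Would a written rule do better?** The natural candidate counts every reaction as a drug reaction unless it is probably or definitely related to the regimen on the 7.2 scale. That scale measures relation to the study treatment only. A reaction caused by neither drug nor regimen would be counted as a drug reaction by default, contrary to 13.1. Such causes are possible: Section 1.1 records chemotherapy and radiation, and Section 3.1 allows participation in other therapeutic trials. Setting the cut so that a possible relation to the regimen still counts against the drug is also a matter of judgement. Adding a proportion of children who stopped bleach to 13.7.1 would describe tolerability and leave the primary result unchanged.

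**The case for a change.** The best case for a change is that 13.1 shows intent but gives no way to carry it out. Skin examinations are done by dermatologists and trained research staff (Section 11.1.4) at three sites, and the 6-week visit may be virtual (Section 10). Nothing says who settles the cause or how a mixed case counts. In a descriptive trial this one proportion is the main product, so its numerator should be clear, and the ambiguity is greatest if the regimen works. In Section 13.6 a regimen reaction can add to the tally even in a child who already has a drug reaction, so all 22 children could be touched. A dated sentence before the pooled analysis would cost little.

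Part of this stands. The attribution procedure is unwritten, 13.5 and 13.6 do not repeat the limit in 13.1, and step 4 shows that the effect would not be trivial if only half the children reacted to the drug.

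The rest is weaker. Regimen reactions are listed as possible, with no rate, so every scenario beyond the background proportion rests on assumed counts. The figure of all 22 is a ceiling, and a lesser regimen reaction need not alter a child's worst grade. Stopping bleach for a skin reaction is documented (Section 5), and adverse events are attributed and reported (Sections 7.2 to 7.4). An analyst can therefore identify regimen reactions and can show the any-cause figure beside the primary one without an amendment.

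**Conclusion.** No change to the plan is called for. The endpoint is already limited by cause in the objectives, Section 11 and Section 13.1. Section 13.5 is a shortened restatement, and the unwritten detail is one that analysts would fill sensibly from records the protocol already requires.

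The effect is 4.5 points per child. It is limited to one child at the only documented proportion, 21/22, where the exact interval is 99.9 − 77.2 = 22.7 points wide. The 13.6-point shift from 17/22 to 20/22 depends on assumed counts. No test, comparator or threshold turns on any of these figures.

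The error that the short wording of 13.5 invites, counting regimen reactions, makes the regimen look worse. The opposite error, putting a drug reaction down to bleach, would flatter it. That is a matter of clinical judgement in an open single-arm trial, and the candidate rule in step 5 would not remove it.

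This conclusion assumes that analysts read 13.5 together with 13.1 and that the records in Sections 5 and 7 are kept as described.

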### **13.6 Analysis of Secondary Endpoints**

In the overall cohort, the minimum, maximum, and quartiles of the number of cutaneous reactions per patient will be calculated.

In the overall cohort: To describe the severity of cutaneous reactions, the proportion of patients at each CTCAE grade of toxicity, and for each grade of the Overall Dry Skin Score (ODS), will be calculated. For each of the following severity scales, the minimum, maximum, and quartiles of the scores will be calculated: Hand-Foot Skin Reaction and Quality of Life Score (HFS-14), Pediatric Quality of Life Inventory (PedsQL), and Children's Dermatology Life Quality Index (CDLQI).

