## 1. OBJECTIVES

Objective #1. To describe the proportion of children with cutaneous reactions to targeted BRAF, MEK, and Pan-RAF inhibitor therapies of a cohort receiving a daily preventative skin care regimen (PSCR) including sun protection, gentle skin care and every other day dilute bleach baths at 6 and 12 weeks.

Objective #2. To describe the number of different cutaneous reactions to targeted BRAF, MEK, and Pan-RAF inhibitor therapies per patient in children receiving daily PSCR including sun protection, gentle skin care and every other day dilute bleach baths at 6 and 12 weeks.

Objective #3. To describe the severity of cutaneous reactions to targeted BRAF, MEK, and Pan-RAF inhibitor therapies for children receiving PSCR including sun protection, gentle skin care and every other day dilute bleach baths at 6 and 12 weeks. using the following severity scales: Common Terminology Criteria for Adverse Events (CTCAE), Overall Dry Skin Score (ODS), Hand-Foot Skin Reaction and Quality of Life Score (HFS-14), Pediatric Quality of Life Inventory (PedsQL), and Children's Dermatology Life Quality Index (CDLQI).

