### **3. PARTICIPANT SELECTION**

#### **3.1 Inclusion Criteria**

- Diagnosed with a CNS or PNS tumor between ages 6 months old -18 years old and will undergo treatment with at least one of the following:
  1. Targeted BRAF inhibitor therapy to treat the tumor
  2. Targeted MEK inhibitor therapy to treat the tumor
  3. Targeted pan-RAF inhibitor therapy to treat the tumor
- Patients must enroll in this trial prior to starting targeted therapy
- Subjects may participate in other studies, including therapeutic trials.
- Ability to comply with PSCR including sun protection, gentle skin care and every other day dilute bleach baths.
- Ability to understand and/or the willingness of their parent or legally authorized representative to sign a written informed consent document.

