#### **3.2 Exclusion Criteria**

- Diagnosed with CNS or PNS tumor at > 18 years old
- No data in medical records regarding treatment exposures
- Treated with a BRAF, MEK or pan-RAF inhibitor in the last three months
- Past or present allergic reaction to bleach
- Past or present allergic reactions to sunscreen and/or creams, lotions, emollients to be utilized in this study

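### Section 13.6 specifies no within-child comparison with baseline for ODS, PedsQL or CDLQI, so the planned tables cannot show how many children developed or worsened on treatment

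*Combined protocol and SAP*

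**What the plan says.** Objective 3 (Section 1) concerns the severity of reactions to the inhibitor in children following the skin regimen with "dilute bleach baths at 6 and 12 weeks. using the following severity scales" that include CTCAE, ODS, HFS-14, PedsQL and CDLQI.

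Section 13.6 gives the analysis. For CTCAE and ODS it is the proportion of patients at each grade ("for each grade of the Overall Dry Skin Score (ODS), will be calculated"). For HFS-14, PedsQL and CDLQI, "For each of the following severity scales, the minimum, maximum, and quartiles of the scores will be calculated". No visit is named, and no change, shift or baseline comparison is mentioned. Nothing else in Section 13 adds one: its opening line promises a descriptive analysis, 13.5 deals with the primary proportion, and 13.7 with its subsections is marked not applicable.

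The data for a paired comparison are planned. In the Study Calendar (Section 10) the row "Severity Scores Completed" is marked at baseline, 6 weeks and 12 weeks. Section 3.1 states: "Patients must enroll in this trial prior to starting targeted therapy". Section 11.1.2 wants baseline evaluations close to the start of treatment and at most 4 weeks before it.

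**The concern.** The objective is about reactions to a drug, but three of the scales carry no attribution to it. ODS grades any dryness; by Appendix A, grade 1 is no more than faint scaling and roughness with a dull look. The CDLQI items ask about the child's skin in general, so they take in skin disease that was already there. PedsQL is described in Section 2 as a global quality-of-life measure, so it can also reflect the tumour and other treatment.

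Eligibility does not remove these sources. Existing skin disease is not an exclusion. Earlier inhibitor use is excluded only if recent ("Treated with a BRAF, MEK or pan-RAF inhibitor in the last three months"). Section 1.1 records chemotherapy and radiation as history where applicable, and "Subjects may participate in other studies, including therapeutic trials".

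The trial has one arm, so the child's own baseline is the only reference inside it. Without a paired summary, the severity tables cannot separate what was present before the drug from what appeared or worsened on it. What is at stake is how those tables can be read. No test, decision rule or sample size depends on them.

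**Working it through.** The plan states no figure on this point, so there is nothing to reproduce beyond the sample size in Section 13.2: 8 + 7 + 7 = 22. One child is 1/22 = 4.5 percentage points.

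**What separate tables at each visit can and cannot show**

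Let n = 22, b = children with ODS of at least 1 at baseline, k = children with ODS of at least 1 at 12 weeks, and m = children with it at both visits. Then:

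- new dryness = k − m
- resolved dryness = b − m
- m lies between max(0, b + k − n) and min(b, k)

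The documents give neither b nor k. Take b = 6 and k = 11 as assumed counts:

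- smallest m = max(0, 6 + 11 − 22) = 0
- largest m = min(6, 11) = 6
- new dryness runs from 11 − 6 = 5 children (5/22 = 22.7%) to 11 − 0 = 11 children (11/22 = 50.0%)
- resolved dryness runs from 6 − 6 = 0 to 6 − 0 = 6 children

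The net rise is 5 in every case (5 − 0 or 11 − 6), and that net figure is all that two separate proportions fix. Only the paired count m gives the number of new cases. The same holds for the continuous scales: the difference between two medians is not in general the median of the differences, and identical quartiles at two visits can mean that no child changed or that improvements and deteriorations cancelled.

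**If only follow-up levels were shown**

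Any number from 0 to k of the k affected children could then have had dryness before the drug. As an illustration, assume a pre-drug prevalence p, a new-onset rate q = 0.3 among children free of dryness, and no resolution. The level at follow-up is p + (1 − p)q and the new-onset share is (1 − p)q.

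| assumed p | level at follow-up | new onset |
|---|---|---|
| 0 | 30% | 30% |
| 0.1 | 37% | 27% |
| 0.3 | 51% | 21% |
| 0.5 | 65% | 15% |

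The level rises across the rows while the new-onset share falls.

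**Is the gain one of precision?**

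Not necessarily. With equal variances at both visits and correlation ρ between them, SD(change)/SD(level) = √(2(1 − ρ)). This is 1.18, 1.00, 0.77 and 0.63 for assumed ρ = 0.3, 0.5, 0.7 and 0.8. Change is less variable than level only if ρ exceeds 0.5. The reason for pairing is to set aside what was there before, not to tighten the estimates.

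**The case against.** The strongest reply is that 13.6 does not exclude baseline. It names no visit, and a table of scores at all three scheduled visits would be consistent with it. That stands: a reader might infer that the plan discards the baseline scores, and the text does not support this. What remains is that even such a table leaves the 5-to-11 range above open.

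Second, Objective 3 asks for severity at two visits and does not mention change. Levels answer that wording in part, which is why the planned summaries should be kept. But the objective ties severity to reactions to the inhibitor, and unattributed levels do not do so.

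Third, change from baseline does not isolate the drug either. This is also right. Section 5 has the skin regimen counselled before anti-cancer therapy begins, so change mixes the inhibitor, the regimen and whatever else happens over 12 weeks. An unchanged ODS may be drug-related dryness offset by emollients. Pairing deals with pre-existing differences only.

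Fourth, materiality is not shown. No baseline values are given; the absence of a skin-disease exclusion does not prove that such children enrol, nor does recording prior chemotherapy or radiation prove that any child had it. This limits how much can be claimed about size. It does not close the gap in the plan. Paired summaries could be added at reporting without new data, but leaving them unspecified allows them to be omitted or chosen selectively.

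**Conclusion.** The point holds in a limited form. Section 13.6 names no visit and specifies no within-child comparison for ODS, PedsQL or CDLQI, although the scores needed are scheduled. Levels alone, at one visit or three, cannot show how many children developed dryness or worsened. In the example this leaves 23% to 50% of the cohort as possible new cases, but the counts of 6 and 11 are assumptions and the true size is unknown.

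The conclusion assumes that the baseline scores are obtained before or at the start of the inhibitor. Sections 3.1 and 11.1.2 together read that way, and Section 5.4 places the first examination at the initiation of treatment.

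Two stronger readings are not supported. The planned summaries are not wrong in themselves; they are incomplete for this objective. And the primary analysis in 13.5 is not touched: only secondary descriptive tables are affected.

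**What to change.** Amend Section 13.6 before analysis as follows.

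- Keep the planned summaries and present them by visit: baseline, 6 weeks, 12 weeks.
- At 6 and at 12 weeks, add the number of children improved, same or worse than their own baseline on ODS.
- At the same visits, add the minimum, maximum and quartiles of within-child change in PedsQL and in CDLQI.
- Give the number of pairs behind each of these. The calendar notes that the "6 week visit may be conducted virtually on request", so footnote how many ODS pairs involve a virtual assessment.
- State that change reflects the inhibitor, the skin regimen and other concurrent effects together and does not isolate the drug effect.
- Show baseline CTCAE skin grades beside the follow-up grades, or say why not. Terms such as dry skin are graded by extent and symptoms without attribution, so the same argument applies.
- HFS-14 can stay as planned, because its items already refer to hand-foot syndrome.

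The cost is SAP wording and a few table columns, with no new data. The downside is that children without a baseline form drop out of the change summaries, and only those.
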